#### Measurement error

The standard error of measurement (SEM) is considered to be a parameter for the amount of measurement error present in an instrument. Using a test-retest design, standard error of measurement (SEM) will be calculated. SEM will be calculated by first creating a variable for the difference between the score obtained during the first and second administration (test score – retest score = *Difference*). The standard deviation of *Difference* in the sample ( $SD_{\text{difference}}$ ) will be calculated.  $SD_{\text{difference}}$  will be divided by the square root of 2 to calculate the SEM. Smallest detectable change (SDC) provides a value for the minimum change that needs to be observed in order to be confident that the observed change is real and not due to measurement error. SDC will be calculated for individuals ( $SDC_{\text{ind}}$ ) and group-level scores ( $SDC_{\text{grp}}$ ).

#### Construct validity

A *priori* hypotheses will be generated to assess the SBQ-LC™’s construct validity. These hypotheses will be refined once the SBQ-LC™ scale structure, as a new PRO, is confirmed. Indicatively:

1. FACIT-Fatigue/– Scores on the FACIT-Fatigue will be positively correlated with SBQ-LC™ scores.
2. Modified MRC Dyspnoea Scale – Scores on the Modified MRC Dyspnoea Scale will be positively correlated with scores on the SBQ-LC™ .
3. Covid-19 core outcome measure for recovery – The Covid-19 core outcome measure for recovery scores will be negatively correlated with SBQ-LC™’s scale scores.
4. PHQ-2 – Scores on the PHQ-2 will be positively correlated with scores on the SBQ-LC™.
5. GAD-2 – Scores on the GAD-2 will be positively correlated with scores on the SBQ-LC™.
6. PCL-2 – Scores on the PLC-2 will be positively correlated with scores on the SBQ-LC™.
7. EQ5D-5L – Scores on the EQ5D VAS will be negatively correlated with scores on the SBQ-LC™.

For continuous scores, Pearson correlations will be used to examine associations. Interpretation of Pearson’s r-values will be based on the guidelines by Cohen (1988): small ( $r = 0.10$  to  $0.29$ ); medium ( $r = 0.30$  to  $0.49$ ); and large ( $r = 0.50$  to  $1.0$ ).

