Participants will complete the questionnaires monthly within a timeframe window of -/+ 7 days. Reminders/notifications will be sent by Atom5™ at Baseline/+2 days/+6 days for the baseline questionnaires and at -7 days/0/+2 days for subsequent ones.

At registration, all participants will be asked to provide the onboarding code provided in their invitation letter. Once participants have registered and provided informed consent, they will then be invited to provide baseline demographic data and report the presence of a wide range of symptoms, quality of life and work/education capability using validated tools via the Atom5™ platform.

Patient-reported outcomes will be assessed using symptom specific measures (Table 1): Symptom Burden Questionnaire-Long COVID (SBQ-LC™), FACIT-Fatigue, modified MRC Dyspnoea Scale, COVID-19 core outcome measure for recovery, Patient Health Questionnaire-2 (PHQ-2), Generalized Anxiety Disorder-2 (GAD-2), Abbreviated PTSD Checklist (PCL-2), and quality of life using the EuroQol-5D (EQ-5D).

The SBQ-LC™ will undergo further validation during the study. The development and initial validation of SBQ-LC™ has been applied for through a separate ethics application to the University of Birmingham Research Ethics Committee since participants will not be recruited via the NHS. The SBQ is a disease-specific, multi-domain instrument that will be used to assess symptom burden and functional status (interference). Respondents will be asked to indicate the presence of a symptom over the last 7 days and then provide an indication of symptom burden by providing a response on a 5-point ordinal scale measuring either symptom severity, symptom frequency, or interference. Higher scores will be indicative of greater symptom burden and interference.

The Functional Assessment of Chronic Illness Therapy –Fatigue Scale (FACIT-Fatigue) is a 13-item measure that assesses self-reported fatigue and its impact upon daily activities and function. It has been validated for use across a range of populations. The FACIT-Fatigue has a 7-day recall period and is scored on a 5-point Likert Scale from “0-Not at all” - to “4-Very much”. Individual items scores are summed (two items of which are reverse scored), multiplied by 13 and then divided by the number of items answered, with a higher score indicating less fatigue and better quality of life. It takes less than 5 min to complete.

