The modified MRC Dyspnoea Scale is a modification to the widely used MRC Dyspnoea scale. The item has a 24-hour recall period and is scored on a 5-point Likert scale from “0 - I only get breathless with strenuous exercise” to “4 - I was breathless when dressing, talking or at rest”. It has a high degree of conceptual overlap with its parent clinical measure, the MRC Dyspnoea scale, which is in wide-scale clinical practice.

The COVID-19 core outcome measure for recovery is a single item intending to measure a return to the pre-illness state. The item has a same day recall period and is scored on a 5-point Likert scale from “0 - Completely recovered” to “5 - Not recovered at all”.

The Euroqol EQ-5D-5L comprises five items plus one visual analogue scale. It has been widely validated and used to assess health outcomes from a wide variety of interventions on a common scale for purposes of evaluation, allocation and monitoring. It is used by the National Institute for Health and Care Excellence (NICE) in health technology assessment. EQ-5D-5L takes only a few minutes to complete and has a same day recall period.

The GAD-2 is a screening tool for generalised anxiety disorder derived from the GAD-7. It comprises the first 2 items of the GAD-7, which are considered as the core anxiety symptoms (“feeling nervous, anxious or on edge”/Not being able to stop or control worrying”). The GAD-2 performs well as a screening tool for three other common anxiety disorders (panic disorder, social anxiety disorder, and PTSD). It has a recall period of two weeks. The GAD-2 has a global score (0-6, no weighting). A higher score indicates an increased likelihood of underlying anxiety disorder. The recommended cut-off score for further investigation is  $\geq 3$ . The GAD-2 has been validated in many studies and has retained the same psychometrics properties of the GAD-7 (86% sensitivity/83% specificity)

The PHQ-2 is a screening tool for depression derived from the PHQ-9. It comprises the first 2 items of the PHQ-9 (depressed mood and anhedonia). The PHQ-2 has a recall period of 2 weeks. It has a global score (0-6, no weighting). A higher score indicates an increased likelihood of an underlying depressive disorder. The recommended cut-off score for further investigation is  $\geq 3$ . The PHQ-2 has been validated in many studies and has shown a sensitivity of 83% and specificity of 92%.

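### Two of the seven indicative construct-validity hypotheses for the SBQ-LC (FACIT-Fatigue and the recovery item) have the opposite sign to the one the protocol's own scoring implies

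*Protocol*

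**What the plan says.** Section 10.2 of the protocol, under Construct validity, lists seven directional hypotheses relating the SBQ-LC to other questionnaires. Hypothesis 1 reads "Scores on the FACIT-Fatigue will be positively correlated with" SBQ-LC scores. Hypothesis 3 reads "The Covid-19 core outcome measure for recovery scores will be negatively correlated with" the SBQ-LC scale scores. The list is introduced as indicative and is to be refined once the SBQ-LC scale structure is confirmed.

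Section 9.1 (Questionnaire data collection) fixes the scoring directions:

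- SBQ-LC: "Higher scores will be indicative of greater symptom burden and interference". The Rasch analysis text in section 10.2 repeats this direction.
- FACIT-Fatigue: 13 items scored 0 (not at all) to 4 (very much). "Individual items scores are summed (two items of which are reverse scored"), and the total is prorated for unanswered items, "with a higher score indicating less fatigue and better quality of life".
- Recovery item: described as a 5-point scale that starts at 0 for complete recovery and ends at "5 - Not recovered at all".

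The Responsiveness paragraph of section 10.2 refers back to the construct-validity hypotheses for the change-score tests.

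**The concern.** A directional hypothesis is informative only if its sign follows from how the two scales are scored. Here two of the predicted signs run against the scoring that the same protocol lays down. Read literally, a strong correlation in the direction that supports the SBQ-LC would be recorded as a failed hypothesis for two comparators that bear directly on Long COVID: fatigue and overall recovery.

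The timing matters as well. Sections 9.5.1 and 10.2 foresee data exports at several time points, including for interim analyses. A sign changed after the correlations have been seen is harder to defend as a priori than one corrected now from the scoring text.

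**Working it through.** The protocol gives no figure to reproduce here, so the check is of signs.

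**Step 1. Expected sign.** If two scales run in the same direction (both higher = worse), a valid SBQ-LC implies a positive correlation. If they run in opposite directions, it implies a negative one. The SBQ-LC is higher = worse (sections 9.1 and 10.2).

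| Hypothesis | Comparator | Direction in section 9.1 | Implied sign | Stated sign | Match |
|---|---|---|---|---|---|
| 1 | FACIT-Fatigue | higher = less fatigue | − | + | no |
| 2 | Modified MRC Dyspnoea | top score is "4 - I was breathless when dressing, talking or at rest", so higher = worse | + | + | yes |
| 3 | Recovery item | 0 recovered to 5 not recovered, so higher = worse | + | − | no |
| 4 | PHQ-2 | higher = depressive disorder more likely | + | + | yes |
| 5 | GAD-2 | higher = anxiety disorder more likely | + | + | yes |
| 6 | PCL-2 | screens positive at 4 or more, so higher = worse | + | + | yes |
| 7 | EQ-5D VAS | not stated; higher = better health assumed | − | − | yes, on that assumption |

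Two of seven signs are reversed; five of seven match.

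**Step 2. Could a different SBQ-LC direction make the list coherent?** No. Hypotheses 2 and 3 use comparators that both run higher = worse, yet predict opposite signs, so no single SBQ-LC direction satisfies both. Reversing the SBQ-LC would repair hypotheses 1 and 3 but break 2, 4, 5 and 6, and also 7 under the VAS assumption.

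**Step 3. How likely is a valid instrument to show the stated sign?** Suppose the true correlation has size |ρ| in the direction that the scoring implies. By the Fisher z approximation, P(sample r has the stated sign) = Φ(−atanh|ρ| × √(n − 3)). Take n = 500, the minimum Long COVID sample in the Study Summary, so √497 = 22.29. The values of |ρ| are assumptions.

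- |ρ| = 0.1: atanh = 0.1003, product 2.237, probability about 0.013.
- |ρ| = 0.3: atanh = 0.3095, product 6.90, probability about 3 × 10⁻¹².
- |ρ| = 0.5: atanh = 0.5493, product 12.25, probability effectively zero.

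These probabilities apply to hypotheses 1 and 3 one at a time.

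**Step 4. Is the scoring text itself sound?** Two points in section 9.1 need attention alongside the signs.

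- FACIT-Fatigue: only two of the 13 items are reversed, which leaves 11 scored upward from not at all to very much. The item wording is not in the protocol. If most of those 11 are statements of fatigue, the recipe as described would make a higher total mean more fatigue, contrary to the direction stated in the same paragraph.
- Recovery item: anchors of 0 and 5 give six integer values, not the five that the label implies. Its direction is clear either way.

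**The case against.** The strongest reply is that the hypotheses are not final. The protocol calls them indicative and provides a step at which they will be refined. That is true, and it means the error can still be corrected without damage. But the stated trigger for refinement is the structure of the SBQ-LC, while the faulty signs arise from the direction of the comparators, which section 9.1 already sets. Confirming the scale structure would not by itself bring the error to light.

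A second reply is that the FACIT-Fatigue item recipe might support the positive sign in hypothesis 1. If so, the recipe contradicts the explicit statement that higher means less fatigue, and the text needs reconciling whichever is correct. Hypothesis 3 has no such ambiguity.

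A third is that the carry-over to responsiveness is inferred: that paragraph cross-refers to the hypotheses but writes out no signs for change scores. This stands, so the carry-over is a possibility and not a certainty.

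Some stronger readings are tempting but not supported:

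- A reader might infer that the SBQ-LC would fail validation as a whole. Section 10.2 also lists Rasch fit, unidimensionality, differential item functioning, internal consistency, test-retest reliability, measurement error, known-groups validity and ROC analysis, none of which is stated to turn on these two signs.
- A reader might set 5/7 = 71% against a pass mark such as 75% of hypotheses confirmed. The protocol states no such rule.
- A reader might infer that a wrongly scored SBQ-LC would pass. A fully reversed one would satisfy hypotheses 1 and 3 but fail the other five (hypothesis 7 under the VAS assumption), matching only 2 of 7, and that pattern would expose the fault.

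**Conclusion.** The point holds in limited form. Two of the seven indicative hypotheses contradict the protocol's own scoring: hypothesis 1 should be negative and hypothesis 3 positive. As written, a valid SBQ-LC would almost certainly fail both; the chance of observing the stated sign for either is about 1.3% at |ρ| = 0.1 and negligible from 0.3 upward.

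This rests on the explicit direction sentences in section 9.1, on 500 participants contributing to the correlations, and on the assumed sizes of ρ. Counting the other five signs as correct rests, for hypothesis 7, on a higher EQ-5D VAS meaning better health. The error is confined to the construct-validity list and possibly the responsiveness tests that refer to it. It is fully recoverable if corrected before analysis.

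**What to change.** Before any SBQ-LC data are analysed:

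1. In section 10.2, state hypothesis 1 as a negative correlation and hypothesis 3 as a positive one, or state explicitly any recoding that reverses those two scores.
2. In the Responsiveness paragraph, say that the same signs apply to change scores.
3. In section 9.1, reconcile the FACIT-Fatigue item scoring with its stated direction, by reference to the instrument's user manual, which that section already says will be followed where available. Do this together with item 1, so that the sign and the scoring recipe agree.
4. In section 9.1, reconcile the recovery item's 5-point label with its 0 to 5 anchors. The known-groups analysis groups participants by this item, so the number of categories matters there too.
5. State the direction of the EQ-5D VAS, so that hypothesis 7 can be checked from the protocol alone.

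The cost is two words in section 10.2, a clause on responsiveness and short corrections to the instrument descriptions. Sample size and schedule are unaffected. Data collection is unaffected too, provided the recovery item as programmed on the platform agrees with the reconciled range.

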#### Known-groups validity

Known-groups validity will be established by comparing SBQ-LC™ scores from individuals with Long COVID with matched controls. A hypothesis testing approach and parametric tests will be used to compare scores on the SBQ-LC™ between groups. A further sub-group analysis will be undertaken whereby Individuals with Long COVID will be grouped using their score rating on the Covid-19 recovery measure as an anchor question. Mean SBQ-LC™ scores will be compared across groups using parametric statistical tests.

#### Criterion validity and establishing cut-off values

Using SBQ-LC™ data from matched controls and participants with Long COVID, we will conduct Receiver Operating Characteristic (ROC) curves analyses. Area Under the Curve (AUC) will be calculated to evaluate the SBQ-LC™'s ability to identify individuals with Long COVID from matched controls. COSMIN guidance recommends an AUC  $\geq 0.70$  as sufficient evidence of criterion validity. The ROC curve will be used to establish cut-off values to support the identification of individuals with Long COVID from the general population.

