### 2.0 Rationale

Approximately 1 in 10 individuals with COVID-19 experience symptoms and impaired quality of life and frequently report experiencing heterogeneous physical and psychological symptoms beyond 12 weeks (“Long COVID”) that can be debilitating. People living with Long COVID have indicated that they are suffering with a

range of symptoms, feel 'abandoned' and 'dismissed' by healthcare providers and receive limited or conflicting advice. The aetiology, pathophysiology and treatments for Long COVID are not well understood, creating an unmet need for the growing number of affected individuals. Although efforts are being made to study Long COVID in hospitalised patients, there is a large unmet need among non-hospitalised individuals. Long COVID may comprise several distinct syndromes yet to be fully characterised.

Existing evidence on Long COVID is based on hospitalised cohorts and non-selected populations that are unlikely to be generalisable to the wider UK population of non-hospitalised individuals. A representative population-based cohort, ideally derived from primary care, is needed to understand the burden of Long COVID, associated disability and impact on work capability. The literature suggests the physical and psychological symptoms of Long COVID are highly diverse and may represent several distinct syndromes. The characterisation of these syndromes using real-world data in combination with patient reported outcomes would aid health services to deliver appropriate interventions to meet these health needs.

The aetiology and risk factors for Long COVID also need further investigation as literature suggests a disproportionately higher prevalence of Long COVID among women, older adults and individuals with specific symptom clusters. One possible explanation for this may relate to differing immunological profiles of individuals who go on to develop Long COVID. For example, older adults with COVID-19 show higher levels of senescent T cells. As these are pro-inflammatory, more likely to be autoimmune and tissue-damaging, their persistence could mediate distinct symptoms in Long COVID among these individuals. Understanding the immunological basis of Long COVID would better enable clinicians to offer targeted therapies.

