### 4.0 Research Outputs and Deliverables

[figure not shown]
1. To establish a population-based representative cohort of 4000 individuals (minimum 2000) with COVID-19, with a minimum of 500 individuals with Long COVID, 500 matched control patients without COVID-19 (control group 1) and 500 matched control patients with COVID-19 but without Long COVID (control group 2). We will capture detailed data on symptoms, quality of life, work capability and objective health measures for individuals with Long COVID and patients in the matched control groups. This will include the development and validation of a new disease-specific PRO of symptom severity and interference for individuals with Long COVID.
2. To develop a new, validated PRO for the measurement of symptom burden in individuals with Long COVID: the Symptom Burden Questionnaire™: Long COVID.

3. To describe distinct Long COVID syndromes and their epidemiology and characterise their immune, inflammatory and proteomic profile, and physical parameters (heart rate intensity, sleep and movement) providing mechanistic understanding of each syndrome and identifying potential therapeutic targets for future evaluation. This will accelerate the identification of potential therapies for Long COVID that are targeted to each syndrome. Based on symptom clusters we will identify up to 200 individuals from the Long COVID cohort, 50 matched control patients without COVID-19, and 50 matched control patients with COVID-19 but without Long COVID to receive bio-sampling and be provided with wearable devices (Garmin Vivosmart4) to measure heart rate, oxygen saturation, step count and sleep quality (BioWear Sub-Study). This will be used in WP2 to deep phenotype Long COVID syndromes.
4. To co-produce a targeted intervention for Long COVID syndromes that can be delivered remotely on a digital platform. This intervention will have patients and carers at the heart of its design and will be based on the best available evidence on Long COVID. It will be designed to be effective, targeted to address symptoms associated with each specific syndrome, acceptable to patients, and scalable.

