## **6.3 Matched controls - Group 2 (50 participants)**

### **6.3.1 Eligibility criteria**

Participants taking part in the study who have had a positive SARS CoV-2 RT-PCR test result in SGSS data linked to CPRD but not reporting symptoms on ATOM5™ beyond 12 weeks from the positive RT-PCR test result will comprise Control Group 1. These control participants will be propensity score-matched to participating Long COVID patients.

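### The SBQ-LC cut-off is derived against matched controls but declared for the general population, which neither control group represents

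*Protocol*

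**What the plan says.** Protocol Section 10.2, under *Criterion validity and establishing cut-off values*, sets the comparison: "Using SBQ-LC™ data from matched controls and participants with Long COVID, we will conduct Receiver Operating Characteristic (ROC) curves analyses". It does not say whether Control Group 1, Control Group 2 or both are meant. An AUC of at least 0.70 is taken "as sufficient evidence of criterion validity". The paragraph ends with the intended use: "The ROC curve will be used to establish cut-off values to support the identification of individuals with Long COVID from the general population".

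The control groups are defined elsewhere:

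- **Control Group 1** (Sections 5.0 WP1 and 6.2) is propensity-matched to COVID-19 patients on demographic, lifestyle, metabolic and comorbidity variables. Anyone with suspected or confirmed COVID-19 is excluded.
- **Control Group 2** (Section 6.3.1) has a positive PCR test, is matched to the Long COVID participants and is defined as "but not reporting symptoms on ATOM5™ beyond 12 weeks from the positive RT-PCR test result".

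The Study Summary and Sections 4.0 and 5.0 plan a minimum of 500 Long COVID participants and 500 in each control group. (The heading of Section 6.3 gives 50 for Control Group 2; the larger figure is used here.) On frequency, Section 2.0 says: "Approximately 1 in 10 individuals with COVID-19 experience symptoms and impaired quality of life".

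**The concern.** A cut-off has the sensitivity and specificity of the people it was estimated on. Here one paragraph names two populations: matched controls for estimation and the general population for use. The general population includes people whom these controls leave out or under-represent. Control Group 1 has no recognised infections, so it has no recovered patients. Control Group 2 has only infected people. Both are matched, so their mix of age, comorbidity and risk factors follows that of the cases rather than that of the population. Specificity in the population could be higher or lower than in the sample; the design cannot tell which, and the protocol has no step that bridges the gap.

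The case share is a second difference. The sample contains far more cases than any population in which the cut-off might be applied, so the share of positives who truly have Long COVID cannot be read from it. A published cut-off carrying a general-population label would invite a use that the study has not tested.

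**Working it through.** **No figure to reproduce.** The protocol gives no sensitivity, specificity, PPV or rule for choosing the cut-off. Its only accuracy figure is the AUC floor of 0.70, so what follows is an illustration.

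**Populations side by side**

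| | Infected people | Uninfected people | Selection |
|---|---|---|---|
| Control Group 1 | none recognised | all | propensity-matched to COVID-19 patients |
| Control Group 2 | all | none | no symptoms beyond 12 weeks; matched to Long COVID cases |
| Declared use | some | most | none |

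**Case share at the minimum sizes**

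- One control group: 500 / (500 + 500) = 50%.
- Both groups: 500 / (500 + 1000) = 33.3%.

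**Prevalence where the cut-off might be used**

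- Among infected people: 10% (Section 2.0).
- General population, low value: 10% of the 4.4 million UK cases in Section 1.0 is 0.44 million. Divided by an assumed population of 67 million, this is 0.66%; populations of 60 to 70 million give 0.73% to 0.63%.
- General population, high value: unrecorded infections would raise the figure, so values up to 5% are also assumed.

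**From AUC to sensitivity and specificity.** Assume an equal-variance binormal ROC curve and the cut-off where sensitivity equals specificity (the Youden point).

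- d = √2 × z(AUC) = √2 × z(0.70) = 0.742.
- Sensitivity = specificity = Φ(d/2) = Φ(0.371) = 0.645.

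**PPV** = se × p / [se × p + (1 − sp)(1 − p)]. For p = 0.10: 0.0645 / (0.0645 + 0.355 × 0.90) = 0.0645 / 0.384 = 16.8%. The other rows follow in the same way; AUC 0.90 (sensitivity = specificity = 0.818) is added as a favourable case.

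| Setting | p | PPV, AUC 0.70 | PPV, AUC 0.90 |
|---|---|---|---|
| Study, one control group | 50% | 64.5% | 81.8% |
| Study, both control groups | 33.3% | 47.6% | 69.2% |
| People with COVID-19 | 10% | 16.8% | 33.2% |
| General population (assumed) | 0.66% | 1.2% | 2.9% |
| General population (assumed) | 2% | 3.6% | 8.4% |
| General population (assumed) | 5% | 8.7% | 19.1% |

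These rows hold sensitivity and specificity constant, so they show the effect of prevalence alone. The effect of the control spectrum on specificity cannot be calculated from the documents.

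**The case against.** The strongest reply is that the PPV figures do not measure the defect. PPV falls at low prevalence for any test, including one whose cut-off came from a perfect random population sample. Case share does not bias sensitivity, specificity or AUC. That is right, and it is why the table is only an illustration. The defect is that the controls cannot supply the specificity that the declared use needs.

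Several stronger readings are tempting, and the documents do not support them:

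- *The study will show a PPV of about two-thirds.* No PPV is stated anywhere. With both control groups pooled, two-thirds is reached only at an AUC between 0.85 and 0.90.
- *The case share is fixed at 33%.* That needs both groups pooled at their minimum sizes. Section 10.2 does not name the group, and Section 5.0 aims for at least 750 Long COVID participants.
- *Control Group 2 omits intermediate cases.* Section 6.1.1 defines Long COVID by COVID-19 symptoms at least 12 weeks from diagnosis, and Section 6.3.1 defines Control Group 2 by the absence of symptoms beyond 12 weeks. The two are essentially complementary, and no middle category is dropped.

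It can also be said that Control Group 1 comes from CPRD, which Section 5.0 (Box 1) describes as representative of the UK. The source may be, but matching and the exclusion of suspected or confirmed COVID-19 mean that the selected group is not. Lastly, the protocol speaks only of supporting identification, and no passage uses the cut-off to classify or manage participants. That limits the harm within the study, but it is the only use stated for the cut-off.

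**Conclusion.** The point holds as a mismatch between the controls used to derive the cut-off and the population for which it is declared. It follows directly from Section 10.2 read with Sections 6.2 and 6.3, and no arithmetic is needed to establish it. The design supports statements about separating Long COVID from these two control groups and, with the whole PCR-positive cohort, from other people who have had COVID-19. It does not support a general-population cut-off.

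On size, at the protocol's AUC floor the illustrative PPV is about 48% to 65% in the study sample, about 17% among infected people, and about 1% to 9% in the general population. These figures rest on a binormal curve, a Youden cut-off, an assumed UK population and assumed prevalences. That predictive values do not transfer is robust to these assumptions; the exact figures are not. A reader should not infer that the estimated sensitivity, specificity or AUC is biased by the case share, or that the direction of any error in specificity is known.

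**What to change.** In Section 10.2, under *Criterion validity and establishing cut-off values*:

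1. Replace the reference to the general population with 'among people with previous COVID-19'.
2. Derive the cut-off in the PCR-positive cohort, comparing Long COVID with all other COVID-19 participants rather than only the matched 500.
3. Report sensitivity and specificity separately against Control Group 1.
4. Give PPV and NPV at the protocol's own 10% prevalence, not read directly from the sample. Even the whole cohort would have 500 / 2000 = 25% cases at the minimum sizes.
5. Make no general-population claim without validation in an unselected sample.

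The cost is a change of wording and a little extra analysis. Table 1.0 already schedules the SBQ-LC at baseline and every month, so no new data are needed unless a general-population claim is pursued. The downside is a narrower stated use, and a PPV that remains modest even among infected people: about 17% at AUC 0.70 and 33% at AUC 0.90 on the assumptions above.
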